#### A5.1.6 Non-cardiovascular death:

Death certificate or equivalent documentation with diagnosis consistent with preterminal documentation and/or information. Death certificate only

*Note*: When no formal written documentation is available, verbal information from relative and/or witness will be admissible and should be recorded on the appropriate study forms.

#### A5.2 NON-FATAL EVENTS

#### A5.2.1 Acute myocardial infarction (Universal definition of myocardial infarction, Thygesen et al Eur Heart J 2007;28:2525-8)

Detection of rise and/or fall of cardiac biomarkers (preferably troponin) with at least one value above the 99th percentile of the upper reference limit (URL) together with evidence of myocardial ischaemia with at least one of the following:

Symptoms of ischaemia

ECG changes indicative of new ischaemia [new ST-T changes or new left bundle branch block (LBBB)] (see glossary)

Development of pathological Q waves in the ECG (see glossary)

Imaging evidence of new loss of viable myocardium or new regional wall motion abnormality.

Elevations of troponin for other causes, in the absence of evidence of myocardial ischaemia, will not be classified as myocardial infarction (see glossary).

For percutaneous coronary interventions (PCI) in patients with normal baseline troponin values, elevations of cardiac biomarkers above the 99th percentile URL are indicative of periprocedural myocardial necrosis. By convention, increases of biomarkers greater than 3x99th percentile URL have been designated as defining PCI-related myocardial infarction. A subtype related to a documented stent thrombosis is recognised.

For coronary artery bypass grafting (CABG) in patients with normal baseline troponin values, elevations of cardiac biomarkers above the 99th percentile URL are indicative of periprocedural myocardial necrosis. By convention, increases of biomarkers greater than 5x99th percentile URL plus either new pathological Q waves or new LBBB, or angiographically documented new graft or native coronary artery occlusion, or imaging evidence of new loss of viable myocardial infarction.

#### A5.2.3 Coronary Revascularisation

Coronary artery bypass graft surgery (CABG) or percutaneous coronary intervention (angioplasty, atherectomy, laser ablation or stenting or any newly introduced invasive method for the management of coronary artery disease).

*Note:* Acceptable documentation will include hospital discharge letters, operation notes or other clinical correspondence documenting performance & date of procedure.

## A5.2.4 Stroke (any event that meets the criteria listed below for one of the following 3 categories of stroke):

Ischaemic stroke (one of the following conditions must be met):

Rapid onset of focal neurological deficit lasting  $\geq$ 24 hours or leading to death plus evidence from neuroimaging (CT or MRI) showing cerebral/cerebellar infarction or no abnormality, or post-mortem examination showing cerebral and/or cerebellar infarction.

Rapid onset of global neurologic deficit (e.g. coma) lasting  $\geq$ 24 hours or leading to death plus evidence from neuroimaging showing cerebral/cerebellar infarction, or post-mortem examination showing infarction.

Focal neurologic deficit (mode of onset uncertain) lasting  $\geq$ 24 hours or leading to death plus evidence from neuroimaging showing cerebral/cerebellar infarction, or post-mortem examination showing infarction.

Primary intercerebral and/or cerebellar haemorrhage (one of the following conditions must be met):

Rapid onset of focal neurologic deficit lasting  $\geq$ 24 hours or leading to death plus evidence from neuroimaging or post-mortem examination showing primary intracerebral and/or cerebellar haemorrhage.

Rapid onset of global neurologic deficit (e.g. coma) lasting  $\geq$ 24 hours or leading to death, plus evidence from neuroimaging or post-mortem examination showing primary intracerebral and cerebellar haemorrhage.

Focal neurologic deficit (mode of onset uncertain) lasting  $\geq$ 24 hours or leading to death, plus evidence from neuroimaging or post-mortem examination showing primary intracerebral and/or cerebellar haemorrhage.

Stroke- mechanism unknown (one of the following conditions must be met):

Rapid onset of focal neurologic deficit lasting  $\geq$ 24 hours or leading to death, without neuroimaging or post-mortem data available.

Rapid onset of global neurologic deficit (e.g. coma) lasting  $\geq$ 24 hours or leading to death, without neuroimaging or post-mortem data available.

Focal neurologic deficit (mode of onset uncertain) lasting  $\geq$ 24 hours or leading to death, without neuroimaging or post-mortem data available.

*Note:* The following **conditions will be excluded** from the defined endpoint of stroke as outlined above:

Primary intracerebral haemorrhage

Primary subarachnoid haemorrhage

Subdural or extradural haematoma

Traumatic intracerebral haemorrhage

Neurologic deficit due to major metabolic or haemodynamic disturbance

Venous sinus thrombosis

Cerebral tumour

Cerebral embolism secondary to infective endocarditis

Any other causes of neurological deficit which, in the opinion of the committee, are not primarily cardiovascular in origin

#### A5.2.5 Carotid revascularisation

Coronary endarterectomy or percutaneous carotid intervention (angioplasty, atherectomy, laser ablation or stenting or any newly introduced invasive method for the management of carotid artery disease).

*Note:* Acceptable documentation will include hospital discharge letters, operation notes or other clinical correspondence documenting performance of procedure & date.

#### A5.2.6 Non-fatal peripheral atherosclerotic events

Hospital-verified acute peripheral arterial ischaemic events. The diagnosis is based on symptoms, clinical findings and/or appropriate radiological investigations.

#### A5.2.7 Peripheral arterial revascularisation

#### Any one of :

Repair of aneurysm or peripheral arterial revascularisation by open surgical or percutaneous techniques (angioplasty, atherectomy, laser ablation or stenting or any newly introduced invasive method for the management of aortic or peripheral arterial disease). Above-ankle amputation for critical limb ischaemia

Chemical or surgical sympathectomy for atherosclerotic peripheral arterial disease.

*Note:* Acceptable documentation will include hospital discharge letters, operation notes or other clinical correspondence documenting performance of procedure & date.

#### A5.2.9 Emergency Hospitalisation for angina

Evidence of emergency hospital admission with chest pain considered due to angina pectoris, plus previous history of documented atherosclerotic coronary artery disease, or documented ischaemic ECG changes during admission, but not meeting criteria for acute myocardial infarction.

#### A5.3 SECONDARY ENDPOINTS

#### A5.3.1 All-cause mortality

Sum of all cardiovascular plus non-cardiovascular deaths.

#### A5.3.2 Fatal peripheral atherosclerotic events

Death occurring within 28 days from the onset of hospital-verified acute peripheral arterial atherosclerotic events. The diagnosis is based on symptoms, clinical findings and/or appropriate radiological investigations.

The Endpoints Committee will be responsible for the classification of all possible study endpoints. The Committee will receive all baseline and end of trial electrocardiograms showing serial changes, information regarding domiciliary visits or hospitalisation associated with possible endpoints, and information on all deaths.

#### A5.4 GLOSSARY

#### A5.4.1 Clinical classification of different types of myocardial infarction

Type 1

Spontaneous myocardial infarction related to ischaemia due to a primary coronary event such as plaque erosion and/or rupture, fissuring, or dissection

Type 2

Myocardial infarction secondary to ischaemia due to either increased oxygen demand or decreased supply, e.g. coronary artery spasm, coronary embolism, anaemia, arrhythmias, hypertension, or hypotension

Type 3

Sudden unexpected cardiac death, including cardiac arrest, often with symptoms suggestive of myocardial ischaemia, accompanied by presumably new STelevation, or new LBBB, or evidence of fresh thrombus in a coronary artery by angiography and/or at autopsy, but death occurring before blood samples could be obtained, or at a time before the appearance of cardiac biomarkers in the blood Type 4a

Myocardial infarction associated with PCI

Type 4b

Myocardial infarction associated with stent thrombosis as documented by angiography or at autopsy Type 5

Myocardial infarction associated with CABG

#### A5.4.2 Causes of elevations of troponin in the absence of overt ischemic heart disease

Cardiac contusion, or other trauma including surgery, ablation, pacing, etc. Congestive heart failure—acute and chronic Aortic dissection Aortic valve disease Hypertrophic cardiomyopathy Tachy- or bradyarrhythmias, or heart block Apical ballooning syndrome Rhabdomyolysis with cardiac injury Pulmonary embolism, severe pulmonary hypertension Renal failure Acute neurological disease, including stroke or subarachnoid haemorrhage Infiltrative diseases, e.g. amyloidosis, haemochromatosis, sarcoidosis, and scleroderma Inflammatory diseases, e.g. myocarditis or myocardial extension of endo-/pericarditis Drug toxicity or toxins Critically ill patients, especially with respiratory failure or sepsis Burns, especially if affecting .30% of body surface area Extreme exertion

#### **A5.4.3 ECG manifestations of acute myocardial ischaemia (in absence of LVH and LBBB)** ST elevation

New ST elevation at the J-point in two contiguous leads with the cut-off points:  $\geq 0.2 \text{ mV}$  in men or  $\geq 0.15 \text{ mV}$  in women in leads V2–V3 and/or  $\geq 0.1 \text{ mV}$  in other leads.

ST depression and T-wave changes

New horizontal or down-sloping ST depression  $\geq 0.05$  mV in two contiguous leads; and/or T inversion  $\geq 0.1$  mV in two contiguous leads with prominent R-wave or R/S ratio >1.

#### A5.4.4 ECG changes associated with prior myocardial infarction

Any Q-wave in leads V2–V3 ≥0.02 s or QS complex in leads V2 and V3.

Q-wave  $\geq 0.03$  s and  $\geq 0.1$  mV deep or QS complex in leads I, II, aVL, aVF, or V4–V6 in any two leads of a contiguous lead grouping (I, aVL,V6; V4–V6; II, III, and aVF).

R-wave  $\geq$ 0.04 s in V1–V2 and R/S  $\geq$ 1 with a concordant positive T-wave in the absence of a conduction defect.

The same criteria are used for supplemental leads V7–V9, and for the Cabrera frontal plane lead grouping.

#### Definitions of non-cardiovascular revascularisations:

#### Non-cardiac procedures

non coronary arterial surgery/intervention unspecified arterial surgery unspecified non coronary angioplasty +/- stent fem-pop bypass/leg artery bypass popliteal or femoral or iliac aneurysm repair aortic aneurysm repair or stent carotid surgery cerebral artery aneurysm surgery or clipping arterial graft reconstruction/excision (not dialysis access) leg artery angioplasty +/- stent renal artery angioplasty +/- stent carotid angioplasty +/- stent non coronary angiogram angiogram of leg/femoral angiogram renal artery angiogram carotid angiogram or arch aortagram Embolectomy

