### 3.1 Primary endpoints

### TRACE RA (all patients): Primary endpoints

The primary comparison will involve Cox regression analyses of "major vascular events" (defined as nonfatal myocardial infarction, non-fatal presumed ischaemic stroke, transient ischaemic attack, any coronary or non-coronary revascularisation or cardiovascular death excluding both confirmed cerebral haemorrhage [ICD I64-99 in the 10th International Classification of Diseases]) and non-coronary cardiac death [ICD I00-I15 and I26-I52] during the scheduled treatment period among all those allocated atorvastatin tablets versus all those allocated placebo tablets (i.e. "intention-to-treat" comparisons).

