#### Primary Endpoints

Cardiovascular death (excluding definite haemorrhagic stroke (ICD 10: I62-67; and non-coronary cardiac death (I00- etc), non-fatal myocardial infarction, non-fatal stroke or any coronary or non-coronary revascularisation. This will comprise the following, as defined in the subsequent paragraphs:

Coronary heart disease death Fatal presumed ischaemic stroke Other atherosclerotic vascular death Myocardial infarction Myocardial infarction Nonfatal stroke Transient ischaemic attack -a mild cerebrovascular stroke with reversible symptoms that last from a few minutes to several hours Coronary revascularization Non-coronary revascularization (see below for definitions)

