#### Amputations

amputation of leg above knee amputation below knee amputation amputation of foot amputation of toe amputation of arm

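### Appendix 5 gives two incompatible definitions of non-coronary revascularisation, a primary-endpoint component; one of them admits diagnostic angiograms and amputations without a stated ischaemic cause

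*Protocol*

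**What the plan says.** Section 3.1 of the protocol counts "any coronary or non-coronary revascularisation or cardiovascular death" among the primary components. Appendix 5, under Primary Endpoints, repeats the component as "Non-coronary revascularization (see below for definitions". Two sets of definitions then follow.

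- **Numbered definitions.** A5.2.3 covers coronary, A5.2.5 carotid and A5.2.7 peripheral revascularisation. A5.2.7 accepts "Repair of aneurysm or peripheral arterial revascularisation by open surgical or percutaneous techniques", sympathectomy for atherosclerotic disease, and "Above-ankle amputation for critical limb ischaemia". A5.2.5, under its carotid heading, begins "Coronary endarterectomy or percutaneous carotid intervention".
- **Closing list.** The block headed Definitions of non-cardiovascular revascularisations names bypass, angioplasty, stenting, aneurysm repair, carotid surgery and embolectomy. It also names "non coronary angiogram angiogram of leg/femoral angiogram renal artery angiogram carotid angiogram or arch aortagram". Next to it, under the heading Amputations, stands "amputation of leg above knee amputation below knee amputation amputation of foot amputation of toe amputation of arm".

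Appendix 5 gives classification to an independent committee, which may use WHO MONICA or another method it prefers. Section 6.4 counts confirmed primary events towards closure of the trial. Appendix 11.5 records that definitions of non-coronary revascularisations were added to Appendix 5 when this component entered the endpoint.

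**The concern.** An angiogram or aortogram is a diagnostic procedure. On the closing list it stands beside stenting and bypass with no condition attached, so a leg angiogram without intervention is an event under that list and not under A5.2.7. Amputation of a toe is named in one place and falls outside the other.

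Three things are at stake. The analysis is of time to first event (Section 10.4), so a listed diagnostic procedure could replace a later genuine event or bring its date forward. Events that treatment does not affect pull the hazard ratio towards 1. Because the trial may close on an event count (Section 6.4), they also bring closure forward. The secondary endpoint of any arterial revascularisation (Section 3.2) carries the same ambiguity.

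**Working it through.** **Which text applies.** Set side by side:

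| Procedure | Closing lists of Appendix 5 | A5.2.7 |
|---|---|---|
| Leg or renal angiogram, no intervention | named | not covered |
| Toe or foot amputation | named, no cause required | not covered (below the ankle) |
| Arm amputation | named, no cause required | not clearly covered; a leg-based wording with critical limb ischaemia required |
| Leg amputation above the ankle | named, no cause required | only for critical limb ischaemia |

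The carotid angiogram and arch aortogram are likewise on the closing list, while A5.2.5 covers carotid interventions only. The reference to definitions below fits both sets, and no rule of precedence is given.

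**Inputs.** 5% two-sided significance and 80% power (Sections 10.1 and 10.4); a 24% reduction after non-compliance, so HR 0.76 (Section 10.1). Event numbers are 434 (Section 10.1), 417 patients with events (Appendix 8, Table 1) and about 370 (Section 6.4). These three do not agree with each other, which is a separate matter; all are shown below. Equal allocation is assumed because no ratio is stated.

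**The plan's own figure.** Schoenfeld: D = 4(1.960 + 0.842)² / (ln 0.76)² = 31.40 / 0.0753 = 417. This matches Table 1.

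**Dilution.** Let f be the share of counted placebo-arm events that treatment does not affect. Then

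HR observed = 0.76(1 − f) + f = 1 − 0.24(1 − f)

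and power = Φ(½√D · |ln HR| − 1.960). The documents give no value of f, so the range is an assumption.

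| f | HR | Events for 80% power | Power at 434 | Power at 417 | Power at 370 |
|---|---|---|---|---|---|
| 0 | 0.760 | 417 | 81.6% | 80.0% | 75.2% |
| 2% | 0.765 | 437 | 79.8% | 78.2% | 73.2% |
| 5% | 0.772 | 469 | 76.9% | 75.2% | 70.2% |
| 10% | 0.784 | 531 | 71.7% | 70.0% | 64.8% |

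Example, f = 5% at 434 events: ½√434 = 10.42; |ln 0.772| = 0.2588; 10.42 × 0.2588 − 1.960 = 0.735; Φ = 76.9%.

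**If the calendar date ends the trial.** The neutral events then come on top of the genuine ones. With 434 genuine events, the placebo arm has 434/1.76 = 246.6 of them, and the total is 434 + 2 × 246.6 × f/(1 − f). For f = 2%, 5% and 10% this gives 444, 460 and 489 events, with power 80.7%, 79.2% and 76.7%, against 81.6% without neutral events.

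**Number of events involved.** The neutral share of all counted events is 2f/(1 + HR). Of 434 events that is about 10, 24 or 49 for f = 2%, 5% or 10%.

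**The case against.** The strongest reply is that the component is called revascularisation, that the numbered paragraphs list interventions only, and that an independent committee classifies every possible endpoint, with only confirmed events counted. A sensible committee would not accept a normal angiogram. This softens the consequence: the documents do not show that such a scan will become a primary event, only that it may if the list is applied literally. It does not remove the conflict. The committee may choose its own method, nothing tells it to leave these entries out, and the written list names them.

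Other objections also have force:

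- **Amputations.** They stand under a heading of their own, so their link to the revascularisation definitions is by position. A reader might infer that the list admits amputations known to be non-ischaemic; in fact it is silent on cause and simply fails to require ischaemia.
- **Treatment effect.** Angiograms may be done for suspected arterial disease, which a statin could influence. HR 1 for the whole group is therefore the unfavourable case. Where an angiogram leads to revascularisation, the event is genuine and only its date moves.
- **Study drug.** A reader might infer that a listed scan or amputation makes a patient stop study medication. Section 7 speaks of patients who have a cardiovascular event and does not refer to this list, so that is not supported.
- **Carotid wording.** A reader might infer that carotid endarterectomy is lost from the endpoint. The word under the carotid heading is an evident slip, and the closing list names carotid surgery.
- **Aneurysm clipping.** Its listing might seem to contradict the exclusion of haemorrhage. The protocol excludes haemorrhagic stroke and death from confirmed cerebral haemorrhage, not every procedure on a cerebral aneurysm.

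**Conclusion.** The point holds as an unresolved contradiction in the definition of a primary component. Two sets of criteria in the same appendix classify the same procedures differently, and neither is given precedence.

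The direction of the effect is clear for any counted event that treatment does not affect: the hazard ratio moves towards 1 and an event-driven closure comes sooner. The size is unknown. It may be negligible (at 2%, power at 434 events drops by under two points) or material (about ten points at 10%), and it shrinks if March 2016 rather than the event count ends the trial. A reader might take the 5% and 10% rows as an estimate of the loss, but the documents give no frequency for these procedures. The figures also rest on equal allocation and on HR 1 for every neutral event.

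The case for acting does not depend on that size. A choice between two endpoint definitions has to be made before unblinding to be free of bias.

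**What to change.** Reconcile the Primary Endpoints list, A5.2.5, A5.2.7, the closing list and the Amputations list of Appendix 5 into one governing definition for endpoint classification, and state that it governs. That definition should:

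- remove the angiogram and aortogram entries;
- keep the therapeutic arterial procedures now named only in the closing list, such as renal artery angioplasty and embolectomy. Making A5.2.3, A5.2.5 and A5.2.7 the sole definition could drop them;
- count an amputation only with an adjudicated ischaemic cause;
- correct the endarterectomy term under the carotid heading.

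Then recheck events already classified against the new text while the trial is still blinded.

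The cost is an amendment to the appendix, the recheck, and somewhat fewer counted events, so the event target may take longer to reach.

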#### Amputations

amputation of leg above knee amputation below knee amputation amputation of foot amputation of toe amputation of arm

## APPENDIX 6: SAFETY OUTCOMES

Clinical laboratory safety parameters are shown below. Haematology and biochemistry will be performed at the local laboratories. All of the safety parameters are subject to routine regular monitoring for safety of the disease-modifying anti-rheumatic drugs (DMARDs). Such monitoring is required as part of routine clinical practice at intervals ranging between 2 weeks and 3 months for all but one DMARDs (the antimalarials). All patients will be questioned about muscle symptoms at each follow-up visit and if new and significant CK will be measured. Only serious adverse events will be recorded. Randomisation codes will be kept securely by participating pharmacists. If deemed necessary by the local investigator the randomisation code can be broken by contacting the local pharmacy.

Abnormalities of haematological and biochemical parameters in this population may be either due to DMARDs or the study drug. The decision of attribution will be left to the managing local investigator.

The study drug should be stopped if:

- Patient has new and significant muscle pains and CK>10xULN,Patient has new and significant muscle pains and ALT/AST >2xULN and CK between 3-10xULN and elevation persists upon retesting.
- Myopathy is diagnosed (muscle pain or weakness AND CK >10 times ULN)
- Elevation of CK to ≥5 times ULN, persisting on retesting 1 week later, should also lead to discontinuation of study medication.

## **APPENDIX 7: INFORMATION ABOUT ATORVASTATIN**

Atorvastatin is generally well-tolerated. Adverse reactions have usually been mild and transient. Less than 2% of patients were discontinued from clinical trials due to side effects attributed to Atorvastatin.

The 'Summary of Product Characteristics' about Atorvastatin will be filed in the TRACE RA site file. Information about Atorvastatin can be found on the electronics medicines compendium section of the (www.emc.medicines.org.uk) website and detailed information about the side effects of the drug is also available in the British National Formulary.

#### Clinical Adverse Experiences (Please see 'Summary of Product Characteristics' for more details)

The most frequent (1% or more) adverse effects associated with Atorvastatin therapy, in patients participating in controlled clinical studies were:

Psychiatric disorders – Insomnia. Nervous System disorders – Headache

Gastrointestinal disorders - Abdominal pain, dyspepsia, nausea, flatulence, constipation, diarrhoea

Musculoskeletal and Connective Tissue Disorders: Myalgia

General Disorders and Administration Site Conditions:

- Asthenia
- Elevated serum ALT levels have been reported in patients receiving Atorvastatin.
- Elevated serum CPK levels > 3 times upper normal (ULN) occurred in 2.5 % of patients on Atorvastatin compared with 3.1% with other HMG-CoA reductase inhibitors in clinical trials.

[Additional adverse events that have been reported in atorvastatin clinical trials are categorised below according to system organ class and frequency. Frequencies are defined as: very common (>10%), common (>1% and <10%), uncommon (>0.1% and <1%), rare (>0.01% and <0.1%) and very rare (0.01%)].

Organ/System Disorder	Event	Frequency
Metabolism & Nutrition	Anorexia Hypoglycaemia Hyperglycaemia	Uncommon Very rare Very rare
Nervous system	Dizziness Paraesthesia Peripheral neuropathy Dysgeusia	Common Uncommon Uncommon Very rare
Psychiatric	Amnesia Depression	Uncommon Uncommon
Blood and Lymphatic System	Thrombocytopenia	Uncommon
Immune System	Allergic reaction (including anaphylaxis	Common
Gastrointestinal	Anorexia Vomiting Pancreatitis	Uncommon Uncommon Uncommon
Hepatobiliary	Hepatitis Cholestatic jaundice Hepatic failure	Rare Rare Very rare
Skin & Subcutaneous Tissue	Alopecia Urticaria Pruritus Rash	Uncommon Uncommon Common Common
Musculoskeletal and Connective Tissue	Muscle cramps Myositis Rhabdomyolysis Myopathy Arthralgia Tendon rupture	Uncommon Rare Rare Uncommon Common Very rare
Eye Disorders	Visual disturbance	Very rare
Ear and Labyrinth Disorders	Tinnitus Hearing Loss	Uncommon Very rare
Reproductive system	Sexual dysfunction Gynaecomastia	Uncommon Very rare
General disorders	Chest pain Back pain Fatigue Angina Malaise Weight gain Peripheral oedema Angioneurotic oedema Interstitial lung disease	Common Common Common Uncommon Uncommon Rare Very rare Very rare

